10.1.2 Recording of Adverse Events

It is the investigator's responsibility to assess whether each untoward event is a clinically significant worsening from baseline, thereby considered an AE. For all AEs, the severity, seriousness, and causality to study drug for each AE as outlined in [Section 10.1.1](#) will be assessed and recorded in the eCRF.

All serious and non-serious AEs are collected once the caregiver/patient has signed the ICF and until the post-treatment follow-up (Visit 12), 28 days after the last dose of study drug.

Any AEs or SAEs that are unresolved at the patient's last AE assessment in the study are followed up by the investigator until resolution or stabilization up to the database lock and recorded in the eCRF. Albireo retains the right to request additional information for any patient with ongoing AE(s) or SAE(s) at the end of the study.

TEAEs that are ongoing at time of discontinuation will be followed up until week 72 by telephone calls every 3 months. No new AEs will be recorded after the patient has permanently discontinued study drug.

TEAEs are defined as any AE that occurs after dosing (Day 1), including new AEs or the worsening of an event after the first dose.

If there is a clinically significant deterioration of a laboratory value/vital sign or other routine study assessment that is associated with a diagnosis, the clinical diagnosis will be reported as an AE and the associated signs and symptoms will be considered additional information unless the sign or symptom is more severe than expected given the diagnosis. For example, if an investigator diagnoses a study patient with hepatitis during the study period, hepatitis would be considered the AE and the concomitant signs and symptoms of abdominal pain, vomiting, and elevated ALT and AST would not be reported separately unless, in the opinion of the investigator, one of these signs or symptoms is more severe than expected and therefore a separate AE assessment is indicated.

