Based on the mode of action of A4250, an IBAT inhibitor, loose stools or diarrhea, and abdominal pain are expected AEs. Non-serious diarrhea and abdominal pain were reported in healthy volunteers and in the investigator-initiated PBC study and in one patient following single dose, but none following multiple dosing in the Phase 2 study in pediatric patients with pruritic cholestatic liver disease. Non-serious diarrhea, vomiting, and abdominal pain were observed in the Phase 3 study in pediatric patients with PFIC.

A4250 taken once daily (QD) at doses up to 200 µg/kg/day, as tested in the Phase 2 study A4250-003, and up to 120 µg/kg/day as evaluated in the Phase 3 study A4250-005, was overall well tolerated. Gastrointestinal (GI) treatment-emergent adverse events (TEAEs) including abdominal pain, abdominal discomfort and diarrhea or loose stool, were associated in time with the onset of the treatment effect of A4250. In general, these AEs were mild to moderate in nature and self-limiting, did not require treatment intervention and were not linked to the degree of reduction of serum bile acid or a rapid reduction in serum bile acid levels.

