10.1 Adverse Events

10.1.1 Definitions and Investigator Assessments

An AE is defined as any untoward medical occurrence in an enrolled patient regardless of causal relationship with study drug. An AE can therefore be any clinically significant unfavorable and unintended sign, symptom, or disease that occurs once a patient is enrolled (ICF is signed) in the study until the patient is discharged from the study, whether or not related to the study drug.

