10.1.1.1 Clinical Significance

Clinical significance is defined as any abnormal finding that results in further clinical investigation(s), treatment(s), or the diagnosis of new condition. Patient-reported events and protocol-mandated laboratory values, vital signs, and physical examination findings can be considered clinically significant (i.e., an AE) if there is a deterioration as compared to baseline. Examples of clinically significant worsening from baseline could include, but is not limited to, events causing withdrawal from the study and events requiring medical intervention outside of the study causing apparent clinical manifestations, or judged relevant by the investigator.

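### Sections 10.1.1, 10.1.1.1 and 10.1.2 disagree on what is recorded as an adverse event, so recording of mild, untreated GI events depends on which sentence an investigator follows

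*Protocol*

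**What the plan says.** Three adjoining parts of the Protocol decide what becomes an AE.

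- **Section 10.1.1** opens broadly: "An AE is defined as any untoward medical occurrence in an enrolled patient regardless of causal relationship with study drug". The next sentence is narrower: "An AE can therefore be any clinically significant unfavorable and unintended sign, symptom, or disease".
- **Section 10.1.1.1** supplies the meaning of the narrower term: "Clinical significance is defined as any abnormal finding that results in further clinical investigation(s), treatment(s), or the diagnosis of new condition". It goes on: "Patient-reported events and protocol-mandated laboratory values, vital signs, and physical examination findings can be considered clinically significant (i.e., an AE) if there is a deterioration" relative to baseline. It closes with a non-exhaustive list of examples that ends "or judged relevant by the investigator".
- **Section 10.1.2** is the working instruction to sites. It is the investigator's "responsibility to assess whether each untoward event is a clinically significant worsening from baseline, thereby considered an AE". Severity, seriousness and causality are then assessed and entered in the eCRF for events that are AEs.

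Two other places bear on the point. Section 10.1.1.3 has a Mild grade for symptoms that are noticed but well tolerated. Section 5.3.1 names loose stools or diarrhea and abdominal pain as expected from the mode of action. Of the gastrointestinal (GI) treatment-emergent adverse events (TEAEs) seen so far it says that, in general, "these AEs were mild to moderate in nature and self-limiting, did not require treatment intervention".

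**The concern.** A definition that takes in every untoward occurrence and a recording rule that takes in only clinically significant worsening cannot both govern what is entered. The rule itself rests on a term with two meanings. The events most exposed are the mild, short-lived GI complaints that the Protocol expects from this drug.

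The opening of Section 10 makes total TEAE incidence part of the primary safety analysis. Section 11.2.2.7 tabulates TEAEs by preferred term and by intensity, and Section 11.2.4 has the DSMB review AE data. All of these use only what sites entered. The study is open-label, has no concurrent control and runs at up to 50 sites. No comparator recorded under the same habits would offset low or uneven recording.

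**Working it through.** No arithmetic applies, because the Protocol states no figure on this point. The check sets the sentences side by side and runs one case through each.

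**The case.** At a telephone contact a caregiver reports new loose stools that were well tolerated and have passed. No test was done, no treatment was given and no new diagnosis was made.

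| Sentence | Is it an AE? |
|---|---|
| 10.1.1, first sentence | Yes |
| 10.1.1, second sentence | Only if clinically significant |
| 10.1.1.1, definition | No: no investigation, treatment or diagnosis followed |
| 10.1.1.1, patient-reported deterioration | It may be: the wording permits but does not require it |
| 10.1.1.1, closing example | Yes, if the investigator judges it relevant |
| 10.1.2, recording rule | Only if clinically significant worsening, so back to 10.1.1.1 |
| 10.1.1.3, Mild grade | Presumes yes |
| 5.3.1, description of earlier studies | Counts such untreated events as TEAEs |

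**Step 1: do the parts contradict each other?** Yes. The first sentence of 10.1.1 has no threshold. The second sentence and 10.1.2 have one. The narrowing starts inside the definition, not only at the recording step.

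**Step 2: does 10.1.1.1 settle the threshold?** No. Its opening sentence is phrased as a definition and gives the answer no. What follows is permissive and can give the answer yes. Two investigators can each follow the text faithfully and record the same event differently.

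**Step 3: are these events relevant to this drug?** Yes. Section 5.3.1 expects them and says that those seen in general needed no treatment intervention. It does not say whether they were investigated, so it does not show that all of them would fail the strict test.

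**Step 4: can anything later recover an event left out?** Not systematically.
- Section 10.1.2 defines a TEAE as an AE with onset or worsening after dosing, so an event that is not an AE cannot be a TEAE.
- The eDiary items in Appendix 2 cover itch or scratching, sleep, tiredness and sleep-inducing medicines. None asks about stools or abdominal pain.
- The diarrhea rules in Section 10.2.2.4 bring to notice episodes that last 7 days or more or come with listed signs such as fever or vomiting. Those call for action and are unlikely to be missed. The gap is at the mild end.

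**Step 5: how large is the effect?** It depends on two quantities: the share of investigators who apply only the strict definition, and the share of events that led to no investigation, treatment or new diagnosis. The documents give neither. The loss is nil if the permissive route is used everywhere. At the other limit, every event of that kind is lost.

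**The case against.** The strongest reply is that the Protocol, read as a whole, points towards recording mild events. Section 10.1.1.1 names patient-reported events expressly, and new diarrhea or abdominal pain reported by a caregiver is a deterioration from baseline. Its examples are open-ended and leave room for judgment. There is a Mild grade, TEAEs are tabulated by intensity, non-serious AEs are collected, and AEs are asked about at every visit and at six telephone contacts. Section 5.3.1 itself tells investigators that these GI complaints are expected AEs. Some judgment about worsening is also unavoidable in a disease with chronic symptoms.

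Most of this stands, and it rules out a stronger reading that a reader might infer: that the Protocol excludes untreated GI events from the AE record. It does not. That conclusion follows only if the definition in 10.1.1.1 is read without the sentences after it.

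The reply does not remove the contradiction. The route that would admit these events is optional, whereas the sentence that would exclude them is worded as the definition. Nor can 10.1.1.1 be set aside as a rule for laboratory and examination findings only, since it names patient-reported events and 10.1.2 applies the test to each untoward event.

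A reader might also infer that TEAE rates here cannot be compared with those of Study A4250-005. The documents do not show that study's AE rule, so this cannot be established. If its wording was the same, the rates may be comparable.

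**Conclusion.** The point holds as an internal inconsistency with a discretionary threshold, and it should be corrected. Sections 10.1.1, 10.1.1.1 and 10.1.2 do not agree on whether an AE is any untoward occurrence or only a clinically significant worsening, and 10.1.1.1 offers both a strict and a permissive test. Recording of mild, self-limiting, untreated GI events can therefore differ between investigators, and TEAE incidence can be too low and uneven across sites.

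The documents give no size for an undercount and do not show that one has occurred. The conclusion rests on the text and on one assumption: that some investigators will follow the definition in 10.1.1.1 rather than the permissive sentences after it. The matter belongs in the Protocol, because no analysis plan can restore events that were never entered.

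**What to change.** Make three wording changes, the same in every country version of the Protocol:

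1. **Section 10.1.1:** keep the broad first sentence as the sole definition of an AE and remove clinical significance as a condition for signs, symptoms and diseases.
2. **Section 10.1.1.1:** limit the clinical-significance test to laboratory values, vital signs and examination findings, and take patient-reported events out of it.
3. **Section 10.1.2:** replace the general test with a statement that any symptom or illness that is new or worse after consent is recorded as an AE, whether or not it is investigated or treated. Keep the investigator's significance judgment for the findings covered by 10.1.1.1.

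Send sites a short reminder with the change. The cost is small: edits to three subsections, more mild AE entries, and a somewhat higher reported TEAE incidence. If the change comes after enrolment has begun, the clinical study report should give its date, so that a rise in mild events is not mistaken for a change in tolerability.

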10.1.3 Recording and Reporting of Serious Adverse Events

Every SAE (regardless of severity and causality) that occurs once the caregiver/patient has signed the ICF and until the post-treatment follow-up (Visit 12), and 28 days after the final dose of study drug, should immediately and not later than within 24 hours of knowledge of the event, be reported by the investigator or delegate in the SAE Report Form.

Report of a SAE must include at least the following information:

- Patient identification information (study number, site number, initials, and date of birth [as per local country requirements for data protection])
- The last study drug administration date
- The diagnosis of the event with the description (or a brief description of signs/symptoms/clinical course if the diagnosis is not available) and the date of onset
- The action used to treat the event (i.e., treatment medications, temporary discontinuation)
- The reason(s) for considering the event serious
- The relationship of the event to the study drug or to the study procedure (e.g., the investigator's assessment of causality)
- A brief narrative of the SAE

Follow-up reports including all new information obtained of the subsequent course of the SAE must be prepared and the information collected in the SAE Report Form submitted to ICON DRUG SAFETY (Pharmacovigilance and Safety Services Department) by e-mail within 24 hours of knowledge of the event.

The pharmacovigilance manager (PVM) may contact the investigator to obtain further information on a reported SAE. The investigator/investigative staff must respond to any request for follow-up information or answers to questions regarding the SAE within the same timelines as for initial reports.

The PVM reports the occurrence of the SAE and follow-up to the Albireo Medical Monitor for medical assessment of the case.

Should an outcome of death occur within the study period or within 28 days after the last administration of study drug, an SAE Report Form should be completed including the main and contributory causes of death.

All SAE reports must be e-mailed to the following e-mail address within **24 hours**:

ICON DRUG SAFETY (Pharmacovigilance and Safety Services Department)

E-mail: PPD

If email is unavailable, SAEs may be transmitted via fax to the following number:

Fax No.: PPD

In a study-related medical emergency situation, when the assigned Medical Monitors for the study cannot be reached by a caller, an on-call physician can be reached 24 hours per day, 7 days per week, via the ICON call center. The following number is a chargeable telephone number allowing a global reach from both landlines and mobile phones and the internet page indicated below contains a list of country-specific toll-free telephone numbers. It should be noted that not all countries globally have access to toll-free numbers as indicated on the “24/7 Medical Help desk” index. Countries without toll-free numbers need to dial the chargeable number as indicated below. Furthermore, toll-free numbers might not be available from mobile phones.

On Call Telephone No.: PPD

<https://icophone.iconplc.com>

10.1.4 Reporting of Suspected Unexpected Serious Adverse Reactions

Suspected unexpected serious adverse reaction (SUSAR) is an SAE that occurs in a patient, the nature or severity of which is not expected per the applicable product information (e.g., the IB for an unauthorized investigational product or summary of product characteristics for an authorized product).

Reporting and tracking of SUSARs will be in accordance with all applicable competent authority regulations. The Ethics Committees and all investigators involved in this study will be informed according to national and international requirements.

10.2 Laboratory Values/Vital Signs/Physical Examinations and Other Safety Assessments

10.2.1 Laboratory Assessments

At the clinic visits indicated in [Table 1](#), samples will be drawn for clinical chemistry, hematology, and urinalysis analyses. The parameters assessed are presented in [Table 3](#).

Blood for AFP will be drawn at Visits 1, 5, 8, and 11. Fat-soluble vitamin levels including vitamins A and E, and 25-hydroxy vitamin D will be assessed at Visits 1, 3, 4, 6, 7, 9, and 10 and INR (surrogate for vitamin K) will be assessed at Visits S-2 (Cohort 2 only), 2, 3, 4, 6, 7, 9, 10, and 12. Patients will fast (water intake only is permissible) for at least 4 hours prior to the collection of samples for vitamin A. Exceptions can be made for infants, <12 months of age, if unable to fast for the full 4 hours. If a patient has any vitamin level(s) that are outside of the reference range, vitamin supplementation adjustments may be required. Target ranges and supplementation strategy guidelines can be found in [Appendix 5](#).

A serum pregnancy test will be performed at Visits S-1 (Cohort 2) and Visit 1 (Cohort 1), and a urine pregnancy test will be collected at all other visits for girls who have reached menarche. If a urine pregnancy test is positive, a serum pregnancy test should be performed to confirm the pregnancy. Study drug administration will be held pending the confirmatory results. If the serum pregnancy test is negative, the patient can resume dosing. If the serum pregnancy test is positive, the patient should be discontinued (see [Section 10.2.9](#)).

All samples will be processed and transported to a laboratory per instructions in the laboratory manual.

The observed values will be recorded and assessed as “normal” or “abnormal not clinically significant” or “abnormal clinically significant”.

For hepatic adverse events and/or hepatic decompensation, a PK sample should be collected as close to the onset of the event as possible (PK samples are not required during the screening period).

Additional safety blood samples may be needed due to follow-up of an abnormal value or analysis failure. The blood samples collected for safety laboratory analysis will be destroyed after the analyses have been completed.

Table 3 Routine Laboratory Parameters

Clinical Chemistry	Hematology	Urinalysis

 • Albumin • ALT • Alkaline phosphatase • AST • Bilirubin – total and conjugated • Calcium • Chloride • Creatinine • Creatine kinase • GGT • Potassium Sodium 	
 • Hematocrit • Hemoglobin • Platelet count • Red blood cell count • White blood cell count and differential (neutrophils, eosinophils, basophils, lymphocytes, and monocytes) 	
 • Blood • Glucose • Ketones • Leukocytes • Nitrates • pH • Protein

10.2.2 Individual Patient Safety Monitoring

10.2.2.1 Liver Monitoring

Strategies to monitor markers of liver disease throughout the study are outlined below where the ULN will be based on central laboratory reference values for age and gender.

For abnormalities classified as hepatic adverse events and/or hepatic decompensation, a PK sample should be collected as close to the onset of the event as possible (PK samples are not required during the screening period).

If isolated transaminase elevations are observed, defined as:

1. Normal bilirubin AND absence of clinical hepatitis symptoms AND
 - ALT or AST $\geq 5 \times$ ULN (if normal at baseline) or an absolute threshold of 800 U/L, whichever comes first
 - OR ALT or AST $\geq 3 \times$ baseline (if abnormal at baseline) or an absolute threshold of 800 U/L, whichever comes first

Then:

- a) Repeat liver profile (AST, ALT, bilirubin, and prothrombin time [PT] or INR) within 2 to 3 days
- b) Evaluate creatine phosphokinase (CPK) and lactate dehydrogenase (LDH)
- c) As needed (for example, persistent ALT/total bilirubin elevation or worsening of liver function), consider evaluation for alternative etiologies

Monitor the patient using close observation found in [Section 10.2.2.2](#).

If any ONE of the following criteria are met:

1. Transaminases (ALT or AST $\geq 3 \times$ baseline or absolute threshold increase of +300 U/L, whichever comes first) AND bilirubin increases to such where total bilirubin $> 2 \times$ ULN if total bilirubin was within normal range at baseline
2. Transaminase elevations alone (ALT or AST $> 5 \times$ ULN for patients that were normal at baseline) or absolute threshold of +300 U/L (for patients starting with transaminases above ULN at baseline) in presence of normal LDH and CPK
3. Total bilirubin increased, unrelated to hemolysis (elevated reticulocyte count) or established genetic diseases, such as Gilbert's syndrome
 - a) Doubling if total bilirubin was < 3 mg/dL (equivalent to 51.3 μ mol/L) at baseline and total bilirubin is greater than $2 \times$ ULN
 - b) OR Increase by > 3 mg/dL (equivalent to 51.3 μ mol/L) if total bilirubin was ≥ 3 mg/dL (equivalent to 51.3 μ mol/L) at baseline
4. INR increase refractory to vitamin K administration
 - a) Increase by > 1.5 if INR was normal at baseline
 - b) OR Increase by > 0.4 if INR was abnormal at baseline
5. Any increase in total bilirubin and transaminases if accompanied by EITHER a symptom of clinical hepatitis (e.g., vomiting, nausea, right upper quadrant pain) OR immunological reaction (rash or $> 5\%$ eosinophilia)

Then:

- a) Interrupt study medication
- b) Initiate drug-induced liver injury work-up for alternative etiologies
- c) Repeat liver profile (AST, ALT, total bilirubin, direct bilirubin) and PT or INR within 48 to 72 hours
- d) Monitor the patient using close observation found in [Section 10.2.2.2](#)
- e) If a patient lives in a remote area, they may be tested locally and the results communicated to the investigator site promptly

